5. STUDY MONITORING AND OVERSIGHT

5.1. SITE MONITORING

Representatives of the University of North Carolina at Chapel Hill will perform assessment locations periodically to assess the data quality and study integrity. Monitors will review study records and directly compare them with source documents, discuss the conduct of the study with the Investigator and verify that the facilities remain acceptable.

5.2. RECORD RETENTION

The site investigator must retain investigational product disposition records, copies of CRFs or eCRFs and source documents for a minimum of four years after the trial is complete or for the maximum period required by Institutional policies, whichever is longer.

6. SAFETY AND ADVERSE EVENTS

It is very important that all staff involved in the study is familiar with the content of this section. The principal investigator of each site is responsible for ensuring compliance with all procedures.

6.1. ADVERSE EVENTS

The definitions of adverse events (AE's), serious adverse events (SAE's) and other significant adverse events (OAE's) are given below. An adverse event is the development of an undesirable medical condition or the deterioration of a pre-existing medical condition following or during exposure to a pharmaceutical product, whether or not considered causally related to the product. An undesirable medical condition can be symptoms (e.g., nausea, chest pain), signs (e.g., tachycardia, enlarged liver) or the abnormal results of an investigation (e.g., laboratory findings, electrocardiogram). In clinical studies, an AE can include an undesirable medical condition

occurring at any time, including run-in or wash-out periods even if no study treatment has been administered.

[name] (PI) will be available on pager and cell phone to all co-investigators to discuss any safety issue that emerges over the course of the study. All adverse events (AEs) occurring during the course of the study are to be documented and reported to the PI. All Serious Adverse Events are reported to the DSMB, IRBs and NIDDK as required. The occurrence of AEs will be assessed during the study and the PIs will follow all AEs to the point of satisfactory resolution. The PI will obtain additional input from [name] (Co-I, Endocrinologist) as needed for evaluating and managing any medical AEs.

6.1.1. Serious Adverse Events

AEs will be assessed to determine if they meet criteria for an SAE. Serious adverse events (SAEs), as defined by the FDA, will be systematically evaluated at each clinic visit. Any SAE will be reported to the IRB, NIDDK, and the FDA. The initial SAE report will be followed by submission of a completed SAE report to all three institutions. In the event that a patient either withdraws from the study or the investigator decides to discontinue a patient due to SAE, the patient will have appropriate follow-up and/or stabilization. Follow-up will continue until the problem requiring hospitalization has resolved or stabilized with no further change expected, is clearly unrelated to study procedures, or results in death. Outcome of SAEs will be periodically reported to NIDDK. A summary of the SAEs that occurred during the previous year will be included in the annual progress report to NIDDK.

The trial period is defined from the time that the informed consent document is signed until 30 days after administration of the last dose of the trial drug. All serious AEs occurring during the trial period (including death due to any cause) or within 30 days after administration of the last dose of the trial drug must be communicated within 1 day of the investigator becoming aware of the event to designated personnel, using the telephone or fax numbers provided in the Study Reference Manual. Any fatal or life threatening AEs must be reported immediately, but no longer than 1 day from the time the investigator becomes aware of the event. A causality assessment must be provided for all serious AEs. Critical follow-up information on serious AE's must be provided as soon as it is available, but no longer than 1 day from the time the investigator became aware of the information. Other essential, but not critical, information may be reported within the following 5 days. Although it is important to report all serious AEs within 1 day, extra measures must be taken to ensure that any serious, unexpected, possibly drug-related AE be communicated immediately.

A serious AE is defined as one that satisfies any of the following criteria:

- Results in death.

- Is immediately life-threatening, including potentially life threatening suicidal behavior or suicidal behavior that results in hospitalization.
- Requires inpatient hospitalization or prolongation of existing hospitalization.
- Results in persistent or significant disability or incapacity.
- Is a congenital abnormality or birth defect.
- Is an important medical event that may jeopardize the subject or may require medical intervention to prevent one of the outcomes listed above.

The causality of SAEs (i.e., their relationship to study treatment) will be assessed by the investigator(s). For further guidance on the definition of a SAE and a guide to the interpretation of the causality question, see Appendices 6 and 7.

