3.2.1. Inclusion Criteria

1. Outpatients with a diagnosis of schizophrenia or schizoaffective disorder as defined by DSM-IV-TR criteria (see Appendix 3 and Appendix 4) and confirmed by the Structured Clinical Interview for DSM-IV (SCID).
2. Duration of psychotic illness must be greater than one year, as defined by having initiated antipsychotic treatment at least 1 year prior to study enrollment.
3. Patients must be 18-65 years of age.
4. Patients must demonstrate adequate decisional capacity to make a choice about participating in this research study and must provide written informed consent to participate.
5. BMI ≥ 27 kg/m²
6. Currently treated with one or a combination of two FDA-approved antipsychotic medications (typical or atypical antipsychotics) AND on that drug regimen for at least 2 months prior to study entry (with stable dosages for at least 1 month).
7. Concomitant medications are allowed if agents and doses are unchanged for at least 1 month prior to study entry and if these medications are not among those excluded in the Exclusion Criteria.
8. Women who can become pregnant must be using an adequate method of contraception to avoid pregnancy throughout the study and for up to 4 weeks after the study in such a manner that the risk of pregnancy is minimized. Acceptable methods include oral, injectable

or implanted contraceptives, intrauterine devices or barrier methods such as condoms, diaphragm and spermicides. Women who can become pregnant must have a negative serum pregnancy test at the Screening Visit.

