3.5.1. Dosing of Study Medications

Subjects will be randomized to 3 groups, see Figure 1.

- Lorcaserin and Metformin-
 - Max dose of 10mg BID of Lorcaserin and max dose of 1,000mg BID of Metformin
- Lorcaserin-
 - Max dose of 10mg BID
- Placebo

Subjects will be randomized to receive lorcaserin 10mg qAM in the MET/LOR and LOR arms or PBO^L qAM. If tolerated, the dose will be titrated up to 10 mg BID at week 1 for 4 weeks. Subjects who tolerate the initial 4 weeks of treatment, in the LOR/MET arm will begin MET 500mg BID at week 4, while the LOR arm and placebo arm will begin PBO^M. At week 6, the LOR/MET arm will have the MET dose increased to 1,000 mg qAM and 500 mg qHS, with corresponding increases in the PBO^M in the other two arms. At week 8 (Visit 6), in the LOR/MET arm, MET is increased to 1,000 mg (2 capsules) BID, with corresponding increases in PBO^M in the other two arms. If this is well tolerated, then subjects continue LOR/MET, LOR/PBO^M, or PBO^L/PBO^M to the end of the study at week 52 (EOS/Visit 17).

Design and titration schedule

[figure not shown]

Figure 1. 52 week randomized, controlled study of lorcaserin/metformin combination treatment, lorcaserin monotherapy or placebo for weight loss in overweight people with schizophrenia. **A.** Subjects are randomized into 3 groups. **B.** Timeline and dose titration for lorcaserin/metformin combination (B.1), lorcaserin monotherapy with placebo to match metformin (B.2), and full placebo arm (B.3) with matching placebos for lorcaserin and metformin, respectively. Subjects continue all study drug until Week 52. SCZ=schizophrenia; BMI=body mass index.

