6.1.2. Death

All deaths occurring within the trial period or within 30 days after the last dose of trial drug is given must be reported within 1 day of the investigator becoming aware of the event.

If an autopsy has been performed, results of the autopsy must be obtained and forwarded along with any available toxicology reports.

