8.2.1.1. Lorcaserin Risks

Lorcaserin has a well-established and generally benign side effect profile. Trials to date that have included over 3,400 subjects exposed to lorcaserin for at least 1 year found the most common adverse events for lorcaserin compared to placebo were headache (17% vs 10%), dizziness (9% vs 4%), nausea (8% vs 5%), and fatigue (7% vs 3%). There were no differences in the occurrence of depression, anxiety or other psychiatric events, including suicidal ideation in studies of lorcaserin at lorcaserin doses up to 20 mg per day. At supratherapeutic doses from short-term Phase I safety studies in non-obese healthy volunteers, doses of 40 and 60 mg per day were associated with increased incidence of euphoria compared to placebo (up to 19% of subjects reported euphoria). In subsequent studies in obese individuals of lorcaserin up to 40 mg per day, reports of euphoria were low (<1%). In the large Phase III trials with lorcaserin limited to 20 mg per day, there was no increase in reports of euphoria or other symptoms of

mania, psychosis or physical/psychological dependence compared to placebo (Smith et al., 2010; Fidler et al., 2011). Because of the potential for lorcaserin to cause euphoria at suprathreshold doses, it has been listed as a Schedule IV controlled substance. There are no data from animal or human studies demonstrating whether lorcaserin can induce physical dependence.

Lorcaserin has not previously been studied in people with schizophrenia. However, 5-HT_{2C} agonists have previously been hypothesized to have potential antipsychotic efficacy by reducing mesocortical dopamine transmission in animal models of psychosis. To test this hypothesis, a recent 6 week RCT examined the safety and efficacy of vabicaserin, a selective 5-HT_{2C} agonist versus olanzapine in 289 people with acutely exacerbated schizophrenia. Vabicaserin was found to produce similar improvements to olanzapine in positive psychotic symptoms, with no benefits on negative symptoms. There was no evidence of significant side effects associated with vabicaserin, including no evidence of psychotic exacerbation or exacerbation of other psychiatric symptoms (Shen et al, 2014). Although not directly testing lorcaserin, these data provide reassurance that 5-HT_{2C} agonists do not pose a significant risk of psychotic exacerbation in people with schizophrenia, and that 5-HT_{2C} agonists as a class may actually exert a therapeutic role for psychosis.

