Appendix 2. Schedule of Events (Week 28 to End-of-Study)

Assessments	WK28 V11	WK32 V12	WK36 V13	WK40 V14	WK44 V15	WK48 V16	WK52 V17 ^a
Demographics							
Vital Signs	X	X	X	X	X	X	X
SCID/Psych + Med Hx/PE							X
Incl/Excl Criteria							
Study Drug Disp + Adherence	X	X	X	X	X	X	X
CGI – Severity	X	X	X	X	X	X	X
BPRS, C-SSRS	X	X	X	X	X	X	X
Substance Use Scale		X			X		X
Alcohol Use Questionnaire		X			X		X
Other Meds Record	X	X	X	X	X	X	X
Adverse Events/Side Effects	X	X	X	X	X	X	X
Behavioral Intervention	X	X	X	X	X	X	X
DXA (Dual X-ray absorptiometry) (UNC ONLY)						X	X*
24 hr food recall assessment, Accelerometry						X	X*
EDE-Q, TFEQ, FCI questionnaires ^c							X
LABS							
Pregnancy test ^b	X	X	X	X	X	X	X
Chemistry							X
CBC w diff							X
LFT ^d , creatinine, eGFR			X				X
Urine Drug Screen							X
Lipid Profile, HbA1c, fasting glucose							X
2hr OGTT							X
Post OGTT insulin							X
Insulin, Leptin, Ghrelin, PYY3-36, GLP-1							X

^a V17 assessments are performed at Wk52 or at any earlier visit at which a subject discontinues for any reason.

^b For female subjects of childbearing potential.

^c Eating Disorder Examination Questionnaire (EDE-Q), Three-Factor Eating Questionnaire (TFEQ), and Food Craving Inventory (FCI)

^d LFTs = AST, ALT, GGT, and total bilirubin

*DXA Scan, 24 hour food recall assessment, and accelerometry are ideally completed at Week 48 but if not done by Week 52 can be done at end of study visit.

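### SAEs and deaths count until 30 days after the last dose, but no routine safety contact is scheduled after Visit 17 or the early stop visit, so new events in that window are captured only passively

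*Combined protocol and SAP*

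**What the plan says.** Section 6.1.1 defines the window: "The trial period is defined from the time that the informed consent document is signed until 30 days after administration of the last dose". Section 6.1.2 uses the same limit for deaths: "All deaths occurring within the trial period or within 30 days after the last dose of trial drug is given must be reported". Appendix 6 repeats the 30 days for fatal events.

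Section 6.1.1 gives one active method of finding SAEs: they "will be systematically evaluated at each clinic visit". Otherwise the duty starts with the investigator's knowledge, since an SAE "must be communicated within 1 day of the investigator becoming aware of the event".

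On dosing, the caption of Figure 1 in Section 3.5.1 says "Subjects continue all study drug until Week 52", and the text of that section equates week 52 with the end of the study and Visit 17. On visits, the footnote to Appendix 2 says "V17 assessments are performed at Wk52 or at any earlier visit at which a subject discontinues for any reason". Section 3.6 has its last telephone call at week 50 and its last session at week 52.

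Inclusion criterion 8 (Section 3.2.1) requires contraception "throughout the study and for up to 4 weeks after the study".

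**The concern.** The plan declares a safety window that extends beyond its own schedule of contacts. Up to Visit 17 or the stop visit, every attending subject is asked about adverse events on a structured form. After that, nobody is routinely asked, although SAEs and deaths still count for up to 30 more days. One reporting window thus contains two kinds of data: solicited reports, then whatever reaches the site.

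Safety and tolerability are Aim 3a, and Section 8.2.1.1 says that lorcaserin had not been studied in schizophrenia before. A reader of the final SAE table would reasonably take a window ending 30 days after the last dose to have been ascertained in the same way throughout. Completeness may also vary with the reason for stopping, because some reasons bring follow-up and others do not. If those reasons differ between arms, so may completeness.

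**Working it through.** The plan gives no figure to reproduce. The check sets the window against the contact schedule and then counts days.

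**Step 1. Routine safety contacts after the last dose**

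| Source | Last routine entry |
|---|---|
| 3.8.19, Appendix 2 (visits) | Visit 17, at week 52 or at the stop visit |
| 3.6 (telephone calls) | Week 50 |
| 3.6 (sessions) | Week 52 |
| 8.2.1.1, 8.2.3 (telephone screen for serotonin syndrome) | Tied to the behavioral calls during the study |

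If the last dose is taken at Visit 17 or the stop visit, the number of routine safety contacts in the next 30 days is 0.

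**Step 2. Does any other provision ask all dosed subjects about new events?**

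- 6.1: recorded AEs are followed until they resolve. Known events only.
- 6.1.1: a subject withdrawn because of an SAE is followed until that problem resolves or stabilizes. Known events only.
- 6.1.3: the outcome of a pregnancy is followed after discontinuation. Known pregnancies only.
- 3.8.19: outstanding DXA (one site), food recall and accelerometry are still to be arranged. This can bring contact, but not for every subject and not as a safety inquiry.
- 3.8.20: unscheduled visits are possible, but nothing prompts one.

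None does.

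**Step 3. Largest gap per subject** (last dose on the day of Visit 17 or the stop visit)

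- Completer, from first dose: 30 / (52 × 7 + 30) = 30/394 = 7.6%.
- Completer, from consent with the full 28-day screening period: 30 / (28 + 364 + 30) = 30/422 = 7.1%.
- Early stopper at week w, from first dose: 30 / (7w + 30). Week 4: 30/58 = 52%. Week 12: 30/114 = 26%. Week 24: 30/198 = 15%.

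**Step 4. Shorter gaps.** If drug was stopped d days before the stop visit, the gap is 30 − d days. Visits from week 12 on are 4 weeks apart, so d can approach 28 for a subject who stops just after one visit and attends the next. The gap is then about 30 − 28 = 2 days. The documents give no expected interval between last dose and stop visit, so the figures in Steps 3 and 5 are maxima.

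**Step 5. Whole trial.** Section 3.2 aims to randomize 90; Section 7.2.1 uses N = 110. Both are shown, with every subject assumed dosed.

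- N = 90: 90 × 30 = 2,700 person-days; 2,700 / 365.25 = 7.4 person-years.
- N = 110: 110 × 30 = 3,300 person-days; 3,300 / 365.25 = 9.0 person-years.

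**Step 6. Events.** The documents give no SAE rate. Assuming 5 to 20 per 100 person-years, the number occurring in the gap would be between 7.4 × 0.05 = 0.4 and 9.0 × 0.20 = 1.8 over all three arms. This is an upper range for events missed, since some would be reported anyway.

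**The case against.** The best defense is that passive capture is still capture. Sections 6.1.1 and 6.1.2 oblige the investigator to report any SAE or death in the window once aware of it. Section 3.2 describes two sites whose investigators work in, or recruit from, the clinics that treat the subjects, so serious events may well become known there. Known events are followed, outstanding procedures can bring subjects back, and a subject who stopped capsules between visits has the full Visit 17 assessments inside the window. The numbers are small, and AEs are only tabulated by arm (Section 7.2). The SAE process is also detailed in a Study Reference Manual that is not part of these documents.

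Much of this stands, and it rules out several stronger readings that a reader might infer:

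- *That all contact ends at Visit 17 or the stop visit, or that the window is unobserved.* Sections 3.8.19, 6.1, 6.1.1 and 6.1.3 provide for later contact, and spontaneous reports count. What is missing is active ascertainment.
- *That capture is worst in subjects who stopped for an adverse event.* Sections 6.1 and 6.1.1 point the other way: those subjects have explicit follow-up.
- *That the gap hides dependence or rebound on stopping lorcaserin.* Section 8.2.1.1 does say "There are no data from animal or human studies demonstrating whether lorcaserin can induce physical dependence". But it also reports no excess of dependence symptoms over placebo in the large Phase III trials at 20 mg per day, and it attributes the controlled-substance listing to euphoria at higher doses. Its remark on a possible benefit for psychosis concerns the class and rests on a trial of another drug. It raises no rebound effect. Non-serious withdrawal symptoms would in any case fall outside a window defined for SAEs and deaths.
- *That pregnancies are under-counted as safety events.* Section 6.1.3 does not treat pregnancy in itself as an AE, and the 4-week contraception rule is an eligibility condition that promises no later check.

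The defense does not supply a routine contact. Site familiarity is described for two of four sites and is not a procedure. A manual that nobody can consult here cannot be counted on to add a contact that the protocol's own schedule omits.

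**Conclusion.** The point holds as a gap in ascertainment: followed as written, the plan detects new SAEs and deaths after Visit 17 or the stop visit only when the investigator learns of them. The size is modest and bounded by the figures above. The share is larger for early stoppers, up to about half of the time since first dose for someone who stops at week 4.

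The day counts assume that the last dose coincides with the last visit and that all randomized subjects are dosed; relaxing either makes the gap smaller. The event range rests on an assumed rate and is only a guide to scale. A difference in completeness between arms is possible but cannot be shown from the documents. The primary and secondary weight comparisons are unaffected. This is a cheap improvement to the data for Aim 3a, not a flaw that endangers the trial.

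**What to change.** Add to Section 3.8.19 and Appendix 2 one telephone contact about 30 days after the last dose for every dosed subject who has not withdrawn consent, completers and early stoppers alike. Use the existing Adverse Events/Side Effects form plus one question on pregnancy, which would also serve the outcome follow-up in Section 6.1.3. State in Section 6.1.1 that SAE ascertainment closes with that call. This is data collection only and changes no treatment rule.

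The cost is an amendment and one short call per subject, by staff who already make the 15 scheduled calls listed in Section 3.6. Database lock moves by about 30 days for the last subject. Under the Section 3.1 timeline that subject finishes at the end of the third quarter of year 4, so the call falls in the fourth quarter, when analysis is to be completed.

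If the call is not added, Section 6.1.1 and the safety tables should at least say that events after the last visit are spontaneous reports only. That corrects the description but does not improve capture.

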6.1.2. Death

All deaths occurring within the trial period or within 30 days after the last dose of trial drug is given must be reported within 1 day of the investigator becoming aware of the event.

If an autopsy has been performed, results of the autopsy must be obtained and forwarded along with any available toxicology reports.

6.1.3. Pregnancy

Pregnancy is an exclusion criterion and women who can become pregnant should use adequate methods of birth control as outlined in the inclusion criteria.

Should a pregnancy occur it must be reported in accordance with the procedures described below. Pregnancy in itself is not regarded as an AE unless there is a suspicion that an investigational product may have interfered with the effectiveness of a contraceptive medication. However, the outcome of all pregnancies (spontaneous miscarriage, elective termination, normal birth or congenital abnormality) must be followed up and documented even if the subject was discontinued from the study. The Adverse Events/Side Affects form will be used for this purpose.

All reports of congenital abnormalities/birth defects are SAEs. Spontaneous miscarriages should also be reported and handled as SAEs. All other outcomes of pregnancy must be reported on the Adverse Events/Side Affects form.

6.1.4. Reporting of Serious Adverse Events

The process flow for reporting serious adverse events along with associated documents and contact information will be presented in the Study Reference Manual to accompany this protocol, as well as the Instructions for Completing the Serious Adverse Event Report. The investigator must provide the minimal information: i.e. subject's initials and date of birth, study ID number, medication, period of intake, and nature of the adverse event and investigator's causality assessment. The other site will also have the opportunity to make contact with the PI for clarifying the event seriousness criteria.

A report of a SAE by telephone must always be confirmed by a written, more detailed report. If a non-serious case becomes serious, this and other relevant information should also be reported.

After initial notification, the PI will perform a medical review of the Serious Adverse Event Report. UNC-CH will be responsible for collecting source documents and confirming the seriousness, relationship to study product and expectedness. Narratives and all supporting documentation will be written and gathered by the PI and sent to NIDDK at the same time.

UNC-CH will forward any follow-up information to the DSMB.

It is the investigator's responsibility to report the AE's which are classified as serious and related to the use of the study drug to the Institutional Review Board (IRB) which has approved the protocol unless otherwise required and documented by the IRB.

All SAEs must be reported, whether or not considered causally related to the study drug. All SAEs will be recorded in the data management system. The investigator is responsible for informing the IRB of the SAE as per local requirements.

